### Previous Studies Assessing the Diagnostic Accuracy of PET

Reference	# patients	PET radiotracer	Sensitivity	Specificity	PPV	NPV	Accuracy
Sampson et al.	102	 Rb	0.93	0.83	0.80	0.94	0.87
Bateman et al.	112	 Rb	0.87	0.93	0.95	0.81	0.89
Marwick et al.	74	 Rb	0.90	1	1	0.36	0.91
Grover-McKay et al.	31	 Rb	1	0.73	0.80	1	0.87
Stewart et al.	81	 Rb	0.83	0.86	0.94	0.64	0.84
Go et al.	202	 Rb	0.93	78	0.93	0.80	0.90
Demer et al.	193	 Rb /  N-am	83	0.95	0.98	0.60	0.85
Tamaki et al.	51	 N-am	0.98	1	1	0.75	0.98
Gould et al.	31	 Rb /  N-am	0.95	1	1	0.90	0.97
Weighted summary	877		0.90	0.89	0.94	0.73	0.90

PPV = positive predictive value; NPV = negative predictive value; Rb = rubidium chloride; N-am = Ammonia

CTA, commonly performed in conjunction with PET, will be a secondary outcome. CTA complements PET in that it can non-invasively quantify anatomical progression of atherosclerotic disease by determining the amount of calcified plaque burden, which is quantified by the coronary artery calcium score (CAC) (33). CAC has been shown to be highly reproducible (33), is strongly correlated with angiographic coronary disease (81), and is a powerful predictor of cardiac events independent of other cardiovascular risk factors (82). The combination of PET/CTA provides information that previously could only be obtained invasively using coronary flow wires and invasive x-ray angiography. This will permit a non-invasive way to evaluate both functional and anatomical adaptations to exercise.

**PET Methods.** A hybrid 64-row PET/CT scanner (GE Discovery VCT, General Electric, WI, USA) will be used in the study. Images will be acquired with simultaneous ECG gating (8 frames/cycle). Heart rate, arterial blood pressure, and 12-lead ECGs will be recorded continuously throughout the evaluation. Heart rate and the arterial blood pressure obtained during the first 2 minutes of each dynamic image will be averaged and used to calculate the rate-pressure product as an index of cardiac work.

*Measurement of myocardial blood flow will be performed at baseline and 1-year in all subjects. Intravenous  $^{13}\text{NH}_3$  will be used as the flow tracer and serial imaging with PET will be performed (83,84). Measurements will be performed at baseline, and after pharmacologic stress with dipyridamole (85). A 20-minute transmission scan will be acquired first for correction of photon attenuation (86). After the first intravenous injection of  $^{13}\text{NH}_3$  (15 to 20 mCi), resting serial transaxial images will be acquired in a sequence consisting of 12 image frames of 10 seconds, 2 frames of 30 seconds, and 1 frame of 900 seconds. Forty-five minutes later, 0.56 mg/kg of dipyridamole IV will be infused over 4 minutes (85).  $^{13}\text{NH}_3$  (15 to 20 mCi) will be injected 4 minutes after the end of the dipyridamole infusion, and serial images will be recorded in the same sequence. Myocardial blood flow at rest and following dipyridamole infusion will be expressed as ml flow/100 g/min. The myocardial perfusion reserve will be calculated as the ratio of the myocardial blood flow during stress (e.g. after dipyridamole) and the myocardial blood flow at rest.*

Commercially available software (Emory tool box) will be used to quantitatively analyze PET myocardial perfusion images. Stress and rest images will be divided according to the 17-segment model (87). The software will define whether ischemia is present and the location and extent of the ischemia relative to the specific myocardial territory (88). The software compares normalized relative radiotracer uptake in reconstructed slices against normal data files. Relative radiotracer uptake on PET images is displayed either as polar plots or bull's eye plots, or as circumferential count distribution profiles. The size of myocardial perfusion defects will be expressed as percentage of the left ventricle. In general, defect extent will be defined as small (5 to 10% of the left ventricle), medium (15 to 20% of the left ventricle), or large (>20% of the left ventricle). Defect severity will be defined as mild, moderate, or severe based on myocardial tracer content compared against normalized data (89). Qualitative interpretation by Drs. [name] and [name] will be used to determine if there were technical issues with regard to processing that impair analysis by the software. *Drs. [name] and [name] will oversee all PET/CTA scans and their interpretation, and they will be blinded to study group when reviewing the images.*

**CT Imaging.** After myocardial perfusion imaging, all patients will undergo calcium scoring and CT angiography (120 kv; 500 mA). First, a prospectively gated low dose sequential CT scan of the heart will be performed for coronary calcium detection and quantification. Patients with pre-scan heart rates above 70 beats per minute will receive intravenous beta-blocker therapy (5 to 15 mg metoprolol tartrate) immediately prior to the CT scan if no contraindications are present. Additionally, 0.04 mg of sublingual nitroglycerin will be administered for coronary dilatation to every patient prior to the scan. ECG-pulsing for radiation dose reduction will be used in all patients. Synchronized to the ECG, CT data sets will be retrospectively reconstructed in mid- to end-diastolic phases and additional phases if needed for optimal coronary artery visualization. Standard reconstruction parameters for slice thickness, field of view, and convolution kernel will be used. For post-processing and image interpretation, the images will then transferred to an external designated workstation (Advantage Workstation, GE).

Comparisons of coronary lesions progression or regression of stenosis and change in calcified and noncalcified plaque area) and functional flow reserve between the two groups at baseline and 1 year post-randomization using CT with contrast will be a secondary outcome. For analysis of anatomy (12), a scoring system will used to quantify disease progression or regression. Stenoses with <10% change in diameter reduction will be classified as unchanged ( $\pm 0$ ). A difference  $\geq 10\%$  between baseline and follow-up will be graded as progression (+1) and a negative difference  $\geq 10\%$  will be graded as regression (-1). Any lesion that necessitates intervention by PCI or bypass surgery will be assigned a grade of +3. Progression from subtotal occlusion to total occlusion (99% to 100%) and spontaneous recanalization will not be graded. In the culprit lesion, an asymptomatic in stent restenosis <50% will be calculated as no change ( $\pm 0$ ). An in-stent restenosis of  $\geq 50\%$  will be rated as progression (+1). An in-stent stenosis  $\geq 50\%$  that required intervention will be classified as progression (+3). A single variable is calculated per patient by adding the grades assigned to the separate stenosis. For analysis of calcified and non-calcified plaque burden (90), the coronary arteries will be divided into 12 segments according to the American Heart Association classification (33). For every coronary artery segment

(identified via side branches) the presence of calcified or noncalcified plaque, both, or neither will be determined using axial and multiplanar reformatted images. To measure plaque volume in each coronary segment, contiguous 1 mm thick cross sectional images of the coronary arteries will be rendered and displayed with a fixed setting (700-HU window, 200-HU level). Plaque areas will be manually traced and volume calculated by multiplying area and slice increment. In the distal segments, analysis of plaque will be limited to the proximal 20 mm. For comparison of calcium scores, total calcium and per artery calcium scores will be compared.

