## **BACKGROUND**

### **Rationale for the Current Proposal**

Despite advances in treatment options for CVD, this condition remains the leading cause of morbidity and mortality in the U.S. and is a major cause of disability in Veterans (1). PCI is the treatment most often used in patients with various manifestations of CAD. It is often used as an intervention for those experiencing *acute coronary syndrome* (ACS), an umbrella term that describes a group of clinical symptoms associated with acute myocardial ischemia. PCI usually involves coronary angioplasty with permanent placement of a stent. This procedure has been shown to reduce symptoms due to CAD and to reduce ischemia (11). In recent years, drug eluting stents (DES) have been shown to reduce the high re-stenosis rate associated with bare metal stents (BMS). However, the cost of DES is 3 to 5 times higher than BMS and requires long term antiplatelet therapy (14). While it is commonly assumed that PCI also reduces mortality, randomized trials have shown that PCI has no effect on 1- to 5-year mortality except in patients being treated for acute myocardial infarction (6,11,15).

There have been major increases in the use of PCI over the last decade, with major costs associated with it. In a recent sub-study of the COURAGE trial, a VA Cooperative study comparing PCI to optimal medical therapy in 2,287 patients with chronic stable angina, the added cost of PCI versus optimal medical therapy was approximately \$10,000, with no benefit in terms of life-years or quality-adjusted life years gained (16). In another sub-study of COURAGE focusing on the effect of PCI on quality of life, it was demonstrated that the cost for 1 patient to have a clinically significant improvement in angina exceeded \$100,000 (17). The COURAGE results demonstrate that it is safe to defer PCI in patients with symptomatic chronic coronary disease, and deferring PCI achieves an appreciable savings in health care expenditures. In light of recent trials demonstrating benefits in coronary vascular function, coronary risk, and cost savings attributable to exercise training in patients with stable symptomatic CAD (12,18,19,20), it is possible that the addition of an exercise program to optimal medical therapy in PCI candidates would result in even better outcomes and cost savings.

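### The 1-year CTA anatomy scoring cannot be blinded to arm as stated, because its rules require the reader to see stents, and no reading order keeps that knowledge away from the PET review

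*Combined protocol and SAP*

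**What the plan says.** All imaging is covered in the PET/CTA Study Protocol section.

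- **Blinding (end of PET Methods).** Two physicians "will oversee all PET/CTA scans and their interpretation", and "they will be blinded to study group when reviewing the images". The statement covers both modalities and both time points.
- **PET quantification (PET Methods).** Commercial software "will be used to quantitatively analyze PET myocardial perfusion images". Qualitative interpretation by two physicians "will be used to determine if there were technical issues with regard to processing that impair analysis by the software".
- **Sequence of acquisition (CT Imaging).** "After myocardial perfusion imaging, all patients will undergo calcium scoring and CT angiography". This fixes the order of scanning. It says nothing about the order of reading.
- **CTA anatomy score (CT Imaging).** Lesions are graded by whether diameter reduction changes by at least 10%, and grades are summed per patient. Stented lesions have their own rules: "In the culprit lesion, an asymptomatic in stent restenosis <50% will be calculated as no change"; restenosis of 50% or more scores +1; and an in-stent stenosis of that degree "that required intervention will be classified as progression (+3"). Any lesion that needs PCI or bypass also scores +3. Plaque areas are traced by hand.
- **What PCI leaves behind (Rationale for the Current Proposal).** "PCI usually involves coronary angioplasty with permanent placement of a stent".
- **How the arms differ (PCI Group).** Schedules and procedures are similar in both arms, except for exercise training and PCI.

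**The concern.** Patients and exercise staff necessarily know the allocation. Blinded image reading is the only masking the documents describe, so it matters whether it can be carried out.

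The score applied at 1 year asks the reader to find the stent, judge the lumen inside it and know whether a further intervention was needed. A reader who does this learns, for most PCI patients, which arm they are in.

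The outcomes read this way depend on judgement: a 10% threshold for change in diameter reduction and manual plaque tracing. They are secondary outcomes, but coronary anatomy is named in the principal objective and in Key Question 1. A report that called the anatomical reading blinded would be inaccurate.

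A second, weaker concern is carry-over to PET. If a physician has already seen the stent when judging whether the software analysis of the 1-year PET was technically sound, that judgement is no longer made without knowledge of arm.

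**Working it through.** This is mainly a check of consistency between sections.

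**Step 1. Can the CTA score be applied blind at 1 year?**

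| Element | Where | What the reader must know |
|---|---|---|
| In-stent grades 0, +1, +3 | CT Imaging | That a stent is present, and in which lesion |
| +3 for PCI or bypass | CT Imaging | That an intervention took place |
| PCI usually leaves a permanent stent | Rationale for the Current Proposal | A stent points to PCI |
| PCI is one of two procedures that differ by arm | PCI Group | PCI points to the arm |

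Taken together, the score cannot be applied to a stented patient without information that usually gives away the arm. The blinding statement and the scoring rules cannot both hold for these scans.

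**Step 2. How reliable a marker is the stent?** Strong but imperfect. Study Population does not list an earlier stent as an exclusion, so an exercise patient may already have one. An exercise patient may also have PCI during the year, and PCI only usually involves a stent.

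**Step 3. Which scans are affected?** Only those at 1 year. Baseline PET/CTA is read to confirm eligibility (Study Population, Recruitment) before randomization, so it cannot reveal the arm.

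**Step 4. Is there a route to the primary endpoint?** The primary outcome is the ratio of stress to rest myocardial blood flow. The one reader judgement described for PET is the qualitative check for processing problems. The plan gives no reading order, no lock on PET results, no written criteria for the check, and no statement of what happens to a scan that fails it. Carry-over is possible, but no step by which it would occur is described.

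**Step 5. Scale.** The plan's own figures (Sample Size Estimates) reproduce:

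- SD of change = √(2 × 0.20² × (1 − 0.65)) = 0.167
- standardized effect = 0.135 / 0.167 = 0.81
- n = 25 per arm at two-sided 0.05 and 80% power
- 25 / (1 − 0.20) = 31.25, rounded up to 32 enrolled per arm

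One scan is 1/25 = 4% of an arm.

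To show sensitivity only, assume the worst case: no true difference, SD 0.167, and the lowest k of 25 change values in one arm set aside. The expected lowest three of 25 standard normal values are −1.965, −1.524 and −1.263. The shift in the group difference is 0.167 × (sum of the k absolute values) / (25 − k). The type I error comes from simulating a two-sample t-test.

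| k | Shift | Share of 0.135 | Two-sided type I error |
|---|---|---|---|
| 1 | 0.167 × 1.965 / 24 = 0.014 | 10% | about 6.6% |
| 2 | 0.167 × 3.489 / 23 = 0.025 | 19% | about 9.4% |
| 3 | 0.167 × 4.752 / 22 = 0.036 | 27% | about 13.5% |

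The documents give no expected number of scans set aside and do not say that any would be. The table shows what a few selective decisions would do at this sample size. It does not estimate bias in this trial.

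**The case against.** The strongest reply is that the primary endpoint is well protected. Flow reserve is a ratio of measured flows. The sentence on technical issues closes a paragraph about software that compares relative tracer uptake with normal files, and it concerns processing. It does not mention accepting or rejecting scans and is not tied to the flow-reserve ratio. This stands, and it rules out three stronger readings that a reader might infer:

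- **That PET and CTA are read together.** The documents give both to the same overseers and say nothing about reading order. CT images go to a separate workstation.
- **That the physicians making the PET technical judgement are the blinded overseers.** Names are removed in both places, so this cannot be established. All that can be said is that the overseers are responsible for every scan.
- **That readers can accept or reject primary-endpoint scans with the arm known.** No such step is described. The plan is silent on what follows a technical problem.

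It can also be said that the stent is an imperfect marker and that the CTA outcome is secondary. Both are true and limit the size of the problem. Neither restores blinding for a score with in-stent categories.

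A last objection is practical: PET cannot all be finalised before any CTA is opened, because baseline CTA decides eligibility a year before the 1-year PET exists. This is correct, so a reading-order rule has to be confined to the 1-year scans.

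**Conclusion.** The concern holds for CTA. The blinding statement cannot be met for the 1-year stenosis grading and plaque tracing in most PCI patients. This follows from the plan's own scoring rules and its own description of PCI, and needs no outside assumption beyond a stent being visible to a reader told to grade inside it.

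For the primary endpoint the finding is narrower. With no reading order set, knowledge of arm from the 1-year CTA could influence the technical judgement on the 1-year PET. The documents neither describe nor exclude this, and its size cannot be estimated from them. They do not support a claim that the primary PET result is unblinded or biased.

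No stated figure changes: the 25 completers and 32 enrolled per arm are unaffected. The point should be settled before 1-year reading starts, because a reading order cannot be imposed once the images have been read.

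**What to change.** 1. **Reading order at 1 year.** Complete and lock each subject's 1-year PET technical-quality decision and perfusion-reserve value before that subject's 1-year CTA is opened. Log any later reprocessing or exclusion with its reason, and report it by arm. Baseline reading for eligibility stays as it is.
2. **Wording in PET Methods.** Replace the general blinding statement with one that says PET reading is blinded to study group and 1-year CTA anatomy scoring is not blinded to stents. Carry the same wording into reports.
3. **Optional sensitivity analysis.** Add a CTA comparison limited to non-culprit lesions. It should not replace the per-patient score, which includes the culprit lesion and is the outcome the plan defines.

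The cost is slightly more reading logistics and a less favourable description of the CTA outcome. No extra scan or patient is needed, and clinical care does not change.

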## RESEARCH DESIGN and METHODS

## Study Population

*Stable patients between the ages of 50 and 70 years who have lesions appropriate for PCI based on American Heart Association/American College of Cardiology criteria will be considered for the study. Only patients with a good prognosis (annual mortality <1% based on VA multivariate scores (56, 57) will be considered. Patients with left main disease or proximal LAD disease will be excluded. Additional exclusion criteria include those with unstable angina, a history of heart failure (EF ≤30%), pacemakers, atrial fibrillation, myocardial infarction within the last 3 months, diabetes, and those with orthopedic problems interfering with the ability to exercise regularly.*

**Recruitment.** *A study flow chart including screening, baseline evaluations, and procedures is presented in Appendix I. Subjects will be recruited from the following populations: 1) patients referred for a clinically-indicated stress myocardial perfusion study (nuclear, echo, or CT); and 2) patients who have a positive exercise test with >1.0 mm ST-segment deviation from baseline on a standard treadmill exercise test, estimated to have a >80% probability of disease based on VA scores (56,57). There are approximately 2,500 patients who undergo these evaluations for CAD at our facility annually, providing a large pool of potential subjects for the study. Potential subjects will be referred for PET/CTA, and baseline PET/CTA findings will confirm patients meet inclusion and exclusion criteria. If the PET/CTA studies show significant ischemia in a moderate to large territory supplied by a significantly diseased vessel, these patients will be recruited for the study.*

*PET is considered the gold standard for stress perfusion imaging. Thus, only patients who have moderate to large areas of moderate to severe perfusion defects will be recruited. In addition, only subjects who have a perfusion defect on PET supplied by a significantly diseased artery on CTA will be recruited. Only subjects actually referred for PCI will be considered for the study. A partial waiver of authorization (per HIPAA) will be obtained in order to access medical records or contact individuals for the purpose of study recruitment. A total of 64 subjects will be recruited; randomization will be stratified by age, exercise capacity, and BMI so that these variables will be matched evenly between exercise intervention and PCI groups.*

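### The secondary CTA anatomy score grades a stented culprit by a different rule from an unstented one, so part of any between-arm difference can come from the rules; a prespecified comparison outside the PCI targets would largely avoid this

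*Combined protocol and SAP*

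**What the plan says.** The scoring rules are in the CT Imaging text of the PET/CTA Study Protocol, which makes the CTA comparison a secondary outcome.

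- **General rule.** A stenosis that changes by less than 10% is graded 0. A difference of at least 10% "between baseline and follow-up will be graded as progression (+1) and a negative difference" of that size as regression (-1).
- **Intervention.** "Any lesion that necessitates intervention by PCI or bypass surgery will be assigned a grade of +3".
- **Stented culprit.** "In the culprit lesion, an asymptomatic in stent restenosis <50% will be calculated as no change". In-stent restenosis of 50% or more is graded +1, or +3 if it required intervention. No -1 is provided.
- **Sum.** "A single variable is calculated per patient by adding the grades assigned to the separate stenosis".
- **Plaque and calcium.** "Plaque areas will be manually traced and volume calculated by multiplying area and slice increment". "For comparison of calcium scores, total calcium and per artery calcium scores will be compared". No rule is given for stented segments.

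On who receives a stent, Study Population states: "Only subjects actually referred for PCI will be considered for the study". Under Screening Process and Informed Consent, these patients are then randomised to exercise or to PCI with usual care. The Background says that PCI usually includes a permanent stent. PET Methods says that the two readers are blinded to group.

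Under Key Question #1, the Statistical Analysis Plan asks about anatomy as well as function. The only method it describes there is repeated measures ANOVA with a baseline versus 1-year factor, given for perfusion reserve. No comparison that leaves out the treated lesion is planned.

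**The concern.** Every patient enters with a lesion referred for PCI, and only one arm is assigned to have it treated. The arm therefore largely decides whether that lesion is judged on change from baseline or on its absolute level at 1 year. Both kinds of grade enter the same sum, so two arms whose culprits behaved alike could have different mean scores. Blinding the readers does not prevent this, because the visible stent selects the rule.

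The intervention grade adds a second route. A later PCI of an exercise-arm culprit scores +3. In the PCI arm the culprit grades of 0 and +1 only make sense if the index procedure is not scored +3, although the text does not say so.

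What is at stake is the anatomical half of Key Question #1, for which this score is the planned measure of progression or regression.

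**Working it through.** **1. The plan's own figure, used only for scale.** Sample Size Estimates gives SD 0.20, pre-post correlation 0.65 and a detectable difference of 0.15 × 0.9 = 0.135.
- SD of change = √(2 × 0.20² × (1 − 0.65)) = 0.167.
- n = 2 × ((1.960 + 0.842) × 0.167 / 0.135)² = 24.02, so 25 completers per arm.
- 25 / 0.8 = 31.25, so 32 enrolled.

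The stated figures reproduce. They concern the PET endpoint; the documents give no mean, SD or power for the anatomy score. With 25 per arm, a one-grade change in one patient moves an arm mean by 1/25 = 0.04.

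**2. Grades for the same course of disease, without intervention or symptoms.** The 10% threshold is read as percentage points of diameter stenosis. Let d be the change from the state just after the assigned treatment, and R the residual stenosis after PCI. R is not in the documents and is assumed to be 0, 10 or 20%.
- Unstented: +1 if d ≥ 10, -1 if d ≤ -10, otherwise 0.
- Stented: +1 if R + d ≥ 50, otherwise 0.

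| R | Narrowing needed for +1, unstented | Narrowing needed for +1, stented (50 − R) | d where unstented minus stented = +1 | d where it is -1 |
|---|---|---|---|---|
| 0% | 10 | 50 | 10 to 49 | none |
| 10% | 10 | 40 | 10 to 39 | -10 only |
| 20% | 10 | 30 | 10 to 29 | -20 to -10 |

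The last two columns list whole points. A stent with residual R cannot regress by more than R, so a negative difference needs R of at least 10%.

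**3. Effect on the mean.** Let g be the share of culprits with narrowing of 10 points or more that the stent rule grades 0, and r the share with regression of 10 points or more. If culprits in both arms followed the same course, the exercise-minus-PCI difference due to the rules alone would be g − r per culprit. Take g and r each between 0 and 20% (assumed).
- R = 0%: r must be 0, so the range is 0 to +0.20 (at the upper end, 5 of 25 patients × 1 grade = 5 × 0.04).
- R of at least 10%: the range extends down to -0.20 (g = 0, r = 0.20). At R = 10% that end requires a regression of exactly 10 points.
- g = r: 0.

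**4. Intervention grade.** If a share c of exercise patients later has PCI of the culprit, and that lesion would otherwise have been graded 0, the arm mean rises by 3c. For c = 10% this is 3 × 0.10 = 0.3. If the lesion would otherwise have been graded +1, it is 2 × 0.10 = 0.2. The index PCI of the same kind of lesion in the other arm adds nothing.

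**5. What such a shift could do.** This was simulated with 25 per arm, a t-test on the sum and no true difference. Assumptions: in-stent stenosis of 50% or more in 5%; each non-target lesion regresses with probability 0.1 and progresses with probability 0.2. With g = 0.20 and r = 0, the nominal 5% test rejects in about 13% of trials with 2 non-target lesions per patient and about 9% with 4. With g = r it rejects in about 5%. All these rates are assumed.

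**The case against.** The stent rule is deliberate, and the scoring paragraph cites the earlier exercise-versus-PCI trial for the score. The rule also has a clear purpose: under the general rule a patent stent would earn -1 from the procedure itself. This stands, and it is why the rule should not simply be deleted. It does not make the two sets of culprit grades comparable.

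The size rests on assumed shares, and it is fair to say that a common course for a stented and an unstented lesion is a construct. PET/CTA is done only at baseline and 1 year, so the state just after PCI is never imaged. This also stands; the arithmetic shows a mechanism and does not estimate a bias.

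A +3 for later PCI records a real event. That is true, but the same procedure on a similar lesion counts in one arm and not in the other, and the decision is made by clinicians who know the arm.

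Finally, the outcome is secondary, and the trial hypothesises improvement in overall anatomy, which a non-target comparison does not measure. Both points limit the weight of the concern and are reasons to add a supporting analysis without replacing the full score.

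**Conclusion.** The concern holds for the secondary CTA anatomy score. The grading rule for the culprit largely follows randomised arm, and the summed score cannot separate the effect of that rule from disease. In the illustration without intervention the rule-only shift is 0 to +0.20 per culprit, with negative values down to -0.20 only if the post-PCI residual is at least 10%. Crossover PCI adds up to 0.3 to the exercise-arm mean for each 10% of patients. The shares, the residual and the crossover rate are assumptions.

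Three stronger readings are not supported.
- *The score favours a particular arm, or inflates the error rate by a known amount.* The stent rule withholds credit for regression and also forgives renarrowing below 50%. The two can cancel, and the documents give no rates.
- *Leaving out one recorded target lesion makes the comparison free of the problem.* Other lesions stented at the index procedure would remain in the score, and so would the +3 grade.
- *The trial's main result is compromised.* Perfusion reserve by PET, the sample size and the cost-effectiveness measure do not use this score.

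No size or direction is claimed for calcium or plaque. For those, the point is only that the target artery is included with no rule for stented segments.

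**What to change.** Make a short addition to the analysis plan before any 1-year scan is read, with the target list recorded before randomisation.

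1. In every patient in both arms, list all lesions and arteries intended for PCI. The information already exists: "only subjects who have a perfusion defect on PET supplied by a significantly diseased artery on CTA will be recruited", and a PCI referral is required.
2. Prespecify a supporting between-arm comparison of the progression score on the remaining lesions only. Name the test: a two-sample or rank test on the one change value per patient, since the score has no baseline value. Tabulate per-artery calcium and segment plaque in non-target arteries in the same way.
3. Use the pre-randomisation list in both arms. Report separately any unlisted lesion stented at the index procedure, with a sensitivity analysis that leaves those lesions out.
4. Report the target lesions separately, with the number of +3 grades by arm. State that the randomised index PCI is not scored +3.
5. Keep the full score for comparability with the earlier trial.

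The cost is plan wording, one extra record per patient and a re-tabulation of readings already planned; no new scan is needed. The supporting comparison answers a narrower question, namely disease outside the target. Patients whose only stenoses are targets add no graded lesion, and the documents do not say how many there will be. The +3 grade outside the target still depends on decisions by clinicians who know the arm, though under one rule for both arms.
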